6.4.5 Sensitivity Analysis

Because of censoring and/or partial data collected on withdrawn infants we will perform the following additional analyses:

- 1. Replicate the primary analysis (H1) to include maternal treatment, stabilization dose, and maternal feeding.
- 2. Given the learning curves needed to be successful at this trial, we will run a sensitivity analysis limited to centers that enrolled greater than 10 infants.
- 3. Replicate the primary outcome analysis to evaluate the effect of being part of Eat Sleep Console
- 4. Perform survival analysis using cutoff at 35 days as censoring indicator.
- 5. If sample size allows, competing risk analysis will be performed using Cox proportional hazard model adjusting for the following: parental withdrawal, physician withdrawal, and treatment failure defined as unable to wean by 35 days of methadone/morphine treatment. This analysis will allow for additional inquiry into the intervention effect on the primary outcome while accounting for competing safety and withdrawal risks.
- 6. For H13, perform a sensitivity analysis for all hypotheses by removing follow ups outside the 22-26 weeks window.

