 - When the clinical team orders opioid escalation, the pharmacy will resume the preceding step of the intervention arm. For example, an infant receiving placebo in the rapid-wean intervention arm will escalate to the last opioid dose (25% of the stabilization dose). The clinical team will maintain the escalated dose for 24 hours, and then follow hospital guidelines to evaluate subsequent changes in drug dose.
 - There are no limits on the number of escalations or resummptions of opioid for either intervention arm.
 - Escalation of the study drug dose is the mechanism to address NOWS signs that require additional pharmacotherapy per each hospital’s specific assessment tool. Spot doses or rescue doses are not part of this trial intervention
- We provide examples of decisions to wean or escalate opioid within a 24-hour period using a hospital guideline and a 12-hour period of protocol guideline (see **Appendix 9**).
- The pharmacy will inform the clinical team when an infant has two dose levels remaining, which will allow the clinical team to be timely with discharge preparation.

Exiting the Study Intervention. Infants will exit the study intervention without unblinding (but remain in the trial) if they have not weaned off study drug by 35 days (inclusive of the 35th day) from the first weaning dose. This represents more than twice the median and mean length of treatment for the morphine arm in the Davis et al. trial (18). This will avoid prolongation of treatment and length of hospital stay due to inability to tolerate the intervention guideline.

Other Criteria to Exit the Intervention.

- Participant who cannot ingest anything by mouth and needs intravenous opioid due to an increase in acuity or need of an operative procedure.
- Unable to take enteral opioid medication
- Participant who has a serious adverse event, including seizures, increased respiratory support, or intravenous fluid for increased stool output.
- Parents or legal guardians wish to withdraw their infant from the intervention.
- The clinical team feels it is in the best interest of the infant to be withdrawn from the intervention.

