4.2.13. Serious Adverse Events

All study personnel will consider adverse events serious if they include any of the following:

- 1) Death

Title: Pragmatic, Randomized, Blinded Trial to Shorten Pharmacologic Treatment of Newborns with Neonatal Opioid Withdrawal Syndrome (NOWS)

Sponsor: National Institutes of Health

- 2) Life threatening adverse event
- 3) Inpatient hospitalization or prolongation of existing hospitalization
- 4) Persistent or significant incapacity or substantial disruption of the ability to conduct normal life functions
- 5) Important medical events that may not result in death, be life-threatening, or require hospitalization, but based on medical judgment may jeopardize the participant and may require medical or surgical intervention to prevent one of the outcomes listed above in this definition.

Participants with serious adverse events will exit the intervention without unblinding the treatment intervention assignment, unless the clinical team considers unblinding essential to the provision of clinical care. The clinical team will assume the care of a participant who exits the intervention, and we will provide the current dose of opioid to the clinical team.

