5.1.4. Analysis of the Primary Hypothesis and Outcome

We will determine the outcome of the primary hypothesis on an intention to treat basis. We will assign infants who exit the intervention at 35 days of methadone/morphine treatment either as 35 days of opioid treatment or we will treat them as a censored value at 35 days. We will determine intervention differences of two means by analyzing the average number of days of opioid treatment from the first

weaning dose to cessation of opioid treatment. We will analyze the data using regression models that will include the intervention as a fixed effect and will include maternal treatment and stabilization dose as covariates. We will include site (hospital) in the model as a random effect. The primary test of interest will be the F-test of the intervention effect, and we will report the intervention difference along with 95% confidence interval (CI).

Because of possible censoring and removal of participants due to intervention failure, we will conduct sensitivity analysis of the primary outcome using several methods. The first sensitivity analysis will replicate the analysis, described above, and include other covariates in the model that were significantly different across the two weaning intervention groups. Sensitivity analyses will also be conducted to evaluate the effects of infants who were and were not part of the Eat Sleep Console trial as a covariate or effect modifier (see **Section 5.2.2**). Another possible sensitivity analysis will include non-parametric and/or survival regression (e.g., negative binomial, median regression, or survival analyses), as there is potential for skewness and censoring in the primary outcome.

Finally, sensitivity analysis will include fitting a competing risks model to the data where the possible competing risk states are weaned, parental withdrawal, physician withdrawal, and treatment failure (unable to wean by 35 days of methadone/morphine treatment). We will fit Cox proportional hazards models to the data to estimate the intervention effect and other covariate effects on “cause-specific hazards.” The analysis of the “cause-specific hazards” will allow for additional inquiry into the intervention effect on the primary outcome while accounting for competing safety and withdrawal risks.

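### SAP 6.4.5 item 5 turns the protocol's competing end states into Cox covariates, and neither document says which state a safety exit belongs to

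*SAP*

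**What the plan says.** SAP 6.4.5 item 5 applies only if "sample size allows". It states that "competing risk analysis will be performed using Cox proportional hazard model adjusting for the following: parental withdrawal, physician withdrawal, and treatment failure", with failure meaning unable to wean by 35 days of methadone or morphine treatment. Its stated purpose is to look further at the intervention effect "while accounting for competing safety and withdrawal risks".

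Protocol 5.1.4 describes the same analysis differently. There, "the possible competing risk states are weaned, parental withdrawal, physician withdrawal, and treatment failure", and the method is "We will fit Cox proportional hazards models to the data to estimate the intervention effect and other covariate effects on" cause-specific hazards. It makes the same claim about safety and withdrawal risks.

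Protocol 4.2.6 lists the ways an infant leaves the intervention. One is "Participant who has a serious adverse event, including seizures, increased respiratory support, or intravenous fluid for increased stool output". A separate bullet reads "The clinical team feels it is in the best interest of the infant to be withdrawn from the intervention". Other bullets cover needing intravenous opioid when nothing can be taken by mouth, being unable to take enteral opioid, and parental withdrawal. Protocol 4.2.13 repeats that "Participants with serious adverse events will exit the intervention without unblinding the treatment intervention assignment".

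**The concern.** Moving from competing states to a model that adjusts for those states changes the analysis. Withdrawal and 35-day failure happen after randomisation, may be affected by the arm, and are alternatives to being weaned. They are outcomes. As covariates they leave a comparison among infants who were weaned, and a shorter weaning time in that subset says nothing about how many infants never reached it.

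The second gap is in the list of states. The analysis is said to cover safety risks, but no listed state is a safety exit. An analyst would have to decide, after seeing data, whether a serious adverse event exit is a physician withdrawal, a censored time or something else.

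Item 5 is the planned analysis meant to separate the reasons for not being weaned, so its states need to be complete and unambiguous.

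**Working it through.** **Why the literal model fails.** Write the weaning hazard as h(t) = h0(t)·exp(β·arm + γ·Z), where Z = 1 for an infant who withdrew or failed. No infant with Z = 1 has the weaning event, so the partial likelihood keeps rising as γ falls towards minus infinity. As exp(γ) goes to 0, those infants carry no weight in any risk set, and β tends to the estimate from weaned infants only.

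This was checked on one simulated trial of 302 infants with a withdrawal indicator as covariate. There were 0 weaning events among 16 withdrawn infants. The coefficient was -25.3 with standard error about 86,000, and the fit did not converge. A second simulation, with a day-35 failure indicator, gave -28 with standard error about 135,000.

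**Size.** The documents give no event count or power for this analysis, so there is no plan figure to reproduce. The only input taken from them is 151 infants per arm. From SAP 3.4 (SD 6.2, difference 2.0, 80% power): 2 × (1.960 + 0.842)² × 6.2² / 2.0² = 150.9, rounded up to 151, or 302 in total. Exit rates and time distributions below are assumptions.

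*Case A: exits are day-35 failures.* Weaning times among successes are 5 + gamma(shape 1.5, scale 4) days in both arms. Failures are censored at day 35 (150 replicates).

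| Failure, rapid v slow | Weaning HR, all infants | Failures removed |
|---|---|---|
| 5% v 3% | 0.94 | 1.01 |
| 10% v 3% | 0.80 | 0.99 |
| 15% v 5% | 0.75 | 1.00 |

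The ratio among weaned infants is 1.00 by construction, so departures from 1.00 in the last column are simulation noise.

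*Case B: exits at random times, independent of weaning.* Weaning times are Weibull with shape 1.5 and a slow-arm median of 9 days. Exit hazards are constant and slow-arm exits are about 3% (300 replicates).

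| Rapid-arm exits, true HR 1.0 | Cause-specific HR | Weaned infants only |
|---|---|---|
| 3% | 1.01 | 1.01 |
| 10% | 1.00 | 1.05 |
| 18% | 1.00 to 1.01 | 1.12 |
| 31% | 1.01 | 1.26 |

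With a true ratio of 1.4, the cause-specific model returned 1.40 to 1.41. The weaned-only fit gave 1.38, 1.43, 1.52 and 1.66 for rapid-arm exits of about 2%, 8%, 15% and 26%.

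In both cases, when the rapid arm has more exits, the shift favours the rapid arm.

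**Exit reasons set against states.**

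| Exit reason (Protocol 4.2.6) | State (Protocol 5.1.4, SAP 6.4.5) |
|---|---|
| Parents or guardians withdraw | Parental withdrawal |
| Clinical team judges withdrawal best | Physician withdrawal |
| Not off study drug by 35 days | Treatment failure, on a different clock |
| Serious adverse event | None named |
| Nothing by mouth, needs intravenous opioid | None named |
| Unable to take enteral opioid | None named |

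**The 35-day clock.** Protocol 4.2.6 counts elapsed time from the first weaning dose and refers to study drug. Protocol 5.1.4 and SAP 6.4.5 refer to 35 days of methadone or morphine treatment. In the rapid arm, study drug includes three placebo levels (Protocol Table 4). An infant on placebo at day 35 is therefore still on study drug but has not had 35 opioid days. SAP 6.1.1 also subtracts long dosing gaps in either arm. The two definitions can classify the same infant differently.

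**The case against.** The best defence is that this is loose paraphrase. The SAP sentence calls itself a competing risk analysis, its closing words track the protocol, and the protocol's specification is sound. A literal fit would also announce itself by failing to converge. As an account of intent this is probably right. But the SAP drops both the weaned event and the cause-specific hazards, and its section 6.4.3 uses the language of adjustment for ordinary covariates. A convergence warning exposes the problem without saying what should replace the model.

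A reader might infer that harm in the rapid arm would disappear from the trial's results. The documents do not support that:

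- SAP 6.4.5 item 4 is a survival analysis censored at 35 days, with no sample-size condition. SAP 5.3 runs it in all randomised infants. In Case A it gives the all-infant ratio of about 0.80.
- The primary outcome is truncated at 35 days, so failures are kept (SAP 6.1.1). In Case A the mean weaning time is 5 + 1.5 × 4 = 11 days, so 10% v 3% failure makes the rapid arm longer by about 0.07 × (35 - 11) = 1.7 days.
- Objective 7 compares safety outcomes by arm in all randomised infants, and escalation and added drugs are also compared.

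A reader might also infer that item 5 cannot account for safety at all. Serious adverse event exits may be coded as physician withdrawal; the documents simply do not say. The gap is inherited from the protocol.

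Finally, a reader might apply the seizure figures in Protocol 5.5.2 (151 × 0.03 = 4.5 and 151 × 0.10 = 15.1) and expect about 5 v 15 infants without a state. That is not supported. The 10% is a stopping threshold, SAP 3.6 reports one infant with a non-related seizure at the 25% mark, and enrolment was ended early.

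**Conclusion.** Item 5 is wrong as written and departs from the protocol it is meant to implement. Followed literally, it has no finite estimate for the exit terms and removes those infants from the arm comparison. The distortion is small when exits are rare or balanced and grows with imbalance. At an assumed 10% v 3% it moves the weaning hazard ratio from about 0.80 to 0.99 (day-35 failures) or from about 1.00 to 1.05 (random-time exits). No exit rate by arm is in the documents, so these figures are illustrations.

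Separately, both documents leave the safety and enteral-route exits unassigned while claiming to cover safety, and the 35-day failure state rests on two different clocks.

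The reach is limited. This is a conditional sensitivity analysis, and SAP 6.4.4 calls everything other than the primary exploratory. The primary mixed model, item 4 and the objective 7 comparisons stand. It should be corrected, but it does not threaten the main result.

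**What to change.** Rewrite SAP 6.4.5 item 5 along the protocol's lines:

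- Event of interest: opioid stopped. Fit cause-specific Cox models with arm as the exposure, and report cumulative incidence of each state by arm. No exit or failure indicator enters as a covariate.
- States: opioid stopped; parental withdrawal; clinician withdrawal; safety or enteral-route exit (serious adverse event, intravenous opioid, unable to take enteral opioid); not weaned at 35 days. If the safety state is sparse, pool it with clinician withdrawal and say so.
- For analysis, define the last state identically in both arms as still receiving opioid at 35 days elapsed from the first weaning dose. Reconcile the study-drug wording of Protocol 4.2.6 with the methadone/morphine wording of Protocol 5.1.4 and SAP 6.4.5. This concerns the coding of the state and leaves the clinical exit rule alone.
- Say how opioid days collected after an exit are used here, since SAP 6.1.1 adds them to the primary outcome when permission is given.

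The cost is a few lines of SAP text. It assumes that exit reasons and dates are recorded. Protocol Section 9 lists a withdrawal form but not its fields, so this should be checked. The small downside is that rare states may need pooling, which gives up some detail.

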6.5 Bayesian Statistical Methods

6.5.1 Statistical Methods

Due to sample size limitation, the primary outcome (H1) and sensitivity analyses (1) and (2) will be analyzed using Bayesian methods in addition to the frequentist analyses to estimate the posterior distribution for all model parameters. Bayesian models will be fit using Markov chain Monte Carlo methods (MCMC) by using software such as PROC MCMC (SAS) or stan (RSTAN/RSTANARM package in R). Model parameter estimates will be generated by fitting three MCMC chains with randomly drawn starting chain. Each chain will involve 1,000 burn-in iterations and 1,000 additional iterations for each chain. Thinning will be used as necessary to reduce autocorrelation among the samples to produce good sampling of the posterior. Trace plots and Gelman-Rubin convergence diagnostics (Rhat <1.1) for all parameters will be used to monitor convergence. For all models, we will report posterior medians and 95% credible intervals (CrI) for the group difference and the probability that a rapid-wean will reduce the days of opioid treatment, compared to a slow-wean intervention.

Primary outcome (H1)

Linear regression model will be used for the primary outcome with treatment group as fixed effect and as hospital random effect. We will use the following priors:

trt effect ~ Normal (
$$\mu = 0, \sigma = 3$$
)
Intercept ~ Normal ($\mu = 0, \sigma = 10$)

All other covariates ~ Normal ($\mu = 0, \sigma = 2$)

Standard deviation of random effect (hospital) $\sim half - noraml (\mu = 0, \sigma = 1)$

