1.8. SAMPLE SIZE AND POWER

The projected effect size is a 2.0 day difference in the duration of opioid treatment between infants randomized to a rapid-wean intervention and infants randomized to a slow-wean intervention. We derived this sample size by using results from a recently completed trial comparing morphine-treated

infants and methadone-treated infants in which the standard deviation was 6.9 days for the morphine-treated infants and 8.0 days for methadone-treated infants. We used a standard deviation of 6.9 days to derive the sample size, anticipating that more infants will be treated with morphine. However, the primary analysis compares treatment regardless of drug used, and we based our sample size calculation irrespective of the proportion of infants treated with morphine or methadone. **Table 2** is for illustrative purposes only, and shows the number of patients treated with morphine and methadone if 70% of infants receive morphine as the primary opioid treatment.

The study will have two intervention arms (rapid-wean and slow-wean) with 251 morphine/methadone treated infants per intervention arm, for a total of 502 morphine/methadone treated infants. This will achieve 90% power to reject the null hypothesis with a significance level of 0.05 using a two-sided two-sample t-test. The null hypothesis will be morphine or methadone treated infants in both arms will have equal means when the population difference in the duration of opioid treatment is 2.0 days with a standard deviation of 6.9 days. It is difficult to predict the proportion of infants treated with either morphine or methadone in the coming years given potential changes in practice. We will recalculate the sample size by considering the standard deviation from pooled data (without unblinding) after 25% of participant accrual.

Table 2. Sample Size

Intervention Arm	Morphine Treated	Methadone Treated	Total
Rapid-wean	176	75	251
Slow-wean	176	75	251
Total	352	150	502

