Subgroup analysis for secondary outcomes 1 and 2: To estimate possible treatment effect heterogeneity for the primary outcome, we will use a Bayesian hierarchical model with main effects and interaction term between intervention group and type of narcotic (morphine or methadone). This approach allows us to specify a priori how likely (or unlikely) it is for subgroup differences to be present and to shrink the subgroup estimates to the overall mean treatment effect. We will specify a model that allows different standard deviations of the outcome for the two subgroups (as observed in Davis et al). Prior distributions for main effects will be the same as for the primary outcome. Neutral and skeptical priors will be used for the interaction terms. Point estimates of treatment effect and 95% credible intervals will be reported for each subgroup along with probability of subgroup treatment differences.

We will analyze secondary binary outcomes with Bayesian logistic regression models, including treatment group, maternal treatment, and stratification dose as covariates, and we will include hospital as a random effect. We will use a neutral prior centered at 1.0 with 95% CrI of 0.33-3.0 (to allow for large range of ORs) for the treatment effect. In the log OR scale, this prior will be normal (0, SD=0.57), and all other priors will be the same as above.

We will analyze secondary outcomes of the total opioid exposure and assessments of maternal well-being, maternal-infant attachment, infant neurobehavioral functioning, infant development, and growth with a similar linear regression model used for the primary outcome.

We will analyze secondary outcome of length of stay with a linear regression model similar to the one used to analyze the primary outcome; however, we will also fit survival analysis models to study the effects of skewness.

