5.2. DESIGN CONSIDERATIONS, SAMPLE SIZE, AND POWER ESTIMATES

5.2.1. Overall Trial Design

During our initial sample size analyses, we considered trial designs that would power two hypothesis tests: one test for the weaning effect of morphine and one test for the weaning effect of methadone. These designs accounted for multiple comparison adjustment (adjusted for two comparisons) and unadjusted comparisons. When we adjusted the two comparisons for multiple comparisons using a Bonferroni adjustment, we rejected a test if the p-value is ≤ 0.025 , and we would require at least 1,032 randomized infants for 90% power. If we did not use an adjustment, then the required sample size was still at least 826 randomized infants. In both cases, the assumed standard deviation was 6.9 days. If the standard deviation is larger, then in both cases the required sample sizes would be even larger. Given the low probability of enrolling around 1,000 infants, we chose a design that would compare weaning interventions regardless of drug used (morphine/methadone). Given that the chosen design would primarily focus on estimating the weaning intervention effect regardless of drugs, we added two secondary analyses examining the intervention effect within each drug (Secondary Outcomes 1 and 2). In addition to frequentist analyses of Secondary Outcomes 1 and 2, Bayesian analyses are planned to derive evidence that may be clinically meaningful from the limited data available for each drug.

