3.4 Sample Size

The projected effect size is a 2.0-day difference in the duration of opioid treatment between infants randomized to a rapid-wean intervention and infants randomized to a slow-wean intervention. The sample size was derived by using results from a recently completed trial comparing morphine-treated infants and methadone-treated infants in which the standard

deviation was 6.9 days for the morphine-treated infants and 8.0 days for methadone-treated infants (see protocol for more details). A standard deviation of 6.9 days was used to derive the sample size, anticipating that more infants will be treated with morphine. However, the primary analysis compares treatment regardless of drug used, and sample size was calculated irrespective of the proportion of infants treated with morphine or methadone.

The study will have two intervention arms (rapid-wean and slow-wean) with 251 morphine/methadone treated infants per intervention arm, for a total of 502 morphine/methadone treated infants. This will achieve 90% power to reject the null hypothesis with a significance level of 0.05 using a two-sided two-sample t-test. The null hypothesis will be morphine or methadone treated infants in both arms will have equal means when the population difference in the duration of opioid treatment is 2.0 days with a standard deviation of 6.9 days. Sample size recalculation was performed in July 2022, using a standard deviation of 6.2 based on data from enrolled infants up to June 2022. It was determined that a sample size of 404 is needed to reach 90% power to reject the null hypothesis with a significant level of 0.05 using a two-sided two-sample t-test, and 302 to reach 80% power. We chose this latter number as our target enrollment.

Subsequently, given continued enrollment challenges faced by this trial, the DSMC and NICHD decided to terminate the trial after December 31, 2023.

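### The SAP leaves out, without explanation, the protocol's Bayesian arm-by-opioid model, so no planned SAP analysis estimates whether the weaning effect differs between morphine and methadone

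*SAP*

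**What the plan says.** **Protocol.** Section 5.1.5 applies the primary-outcome approach to morphine-treated infants alone and then to methadone-treated infants alone. Section 5.1.6 adds, for the same two outcomes: "we will use a Bayesian hierarchical model with main effects and interaction term between intervention group and type of narcotic". That model shrinks the drug-specific effects toward the overall effect, allows a different outcome SD for each drug, uses neutral and skeptical priors on the interaction, and reports the probability that the drug effects differ. Section 5.2.1 gives its purpose: "Bayesian analyses are planned to derive evidence that may be clinically meaningful from the limited data available for each drug".

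**SAP.** Section 6.5.1 limits the Bayesian scope: "the primary outcome (H1) and sensitivity analyses (1) and (2) will be analyzed using Bayesian methods". Section 6.5.2 adds only alternative priors for the primary outcome. Under section 4.1, H2 and H3 are linear mixed models with site as a random effect, tested at two-sided 0.05 (6.4.1). Section 6.4.4 lists interaction analyses by race/ethnicity and sex only, and opioid type is not among the covariates in 6.4.3. The revision history in 1.3 is silent on the change. Section 3.5 nevertheless keeps the effect by specific opioid among the secondary goals.

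**The concern.** The by-drug question is part of the trial's rationale. Protocol 3.3.4 says that a benefit may appear for both drugs, one, or neither. With the interaction model gone, the SAP offers two subset results and no planned comparison between them. Two p-values from subsets of very different size are a poor guide to whether effects differ: the larger subset is more likely to reach significance even when the true effects are equal. A reader could take a significant morphine result beside a non-significant methadone result as evidence that rapid weaning works for one drug only.

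The reason for the model has also grown stronger. SAP 6.5.1 justifies Bayesian methods by limited sample size. That limitation is worst within each drug, which is where the method was left out, and the target has fallen from 502 to 302.

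**Working it through.** **Inputs**
- Effect: "The projected effect size is a 2.0-day difference in the duration of opioid treatment" (SAP 3.4). Two-sided alpha is 0.05, with equal allocation.
- SD at design: "A standard deviation of 6.9 days was used to derive the sample size" (SAP 3.4). SD at recalculation, 6.2: "using a standard deviation of 6.2 based on data from enrolled infants up to June 2022" (SAP 3.4). Methadone SD in the cited trial: "8.0 days for methadone-treated infants" (protocol 1.8).
- Total N: 302, the target in SAP 3.4. Enrollment was then ended by date and the final N is not given.
- Morphine share of the two drugs: 70% (protocol 1.8, illustrative), 76% (survey, 5.3), 86.1% (chart review, 3.3.3), about 87% (3.3.2).
- No dropout is applied, because none is stated.

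**Step 1. Reproduce the plan's figures.** n per arm = 2·SD²·(1.960 + z_power)² / 2².
- SD 6.2, 80% power: 150.9, so 151 per arm and 302 in total, as stated.
- SD 6.2, 90%: 202.0, so 202 per arm and 404, as stated.
- SD 6.9, 90%: 250.1, so 251 per arm and 502, as stated.

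**Step 2. Power within each drug at 302.** n per arm = 302 × share / 2; SE = SD·√(2/n); power comes from the non-central t distribution with non-centrality 2/SE. For a 70% share and SD 6.2:
- Morphine: n = 105.7, SE = 0.853, non-centrality 2.34, power 64.6%.
- Methadone: n = 45.3, SE = 1.303, non-centrality 1.53, power 33.0%.

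**Step 3. Pattern of the two tests when both true effects are 2 days.** The subsets share no infants, so the two tests are treated as independent. P(morphine only) = power_morphine × (1 − power_methadone), and likewise for the other patterns.

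| Morphine share | SD morphine / methadone | Power morphine | Power methadone | Morphine only | Methadone only | Both | Neither |
|---|---|---|---|---|---|---|---|
| 70% | 6.2 / 6.2 | 64.6% | 33.0% | 43.3% | 11.7% | 21.3% | 23.7% |
| 76% | 6.2 / 6.2 | 68.2% | 27.3% | 49.6% | 8.7% | 18.6% | 23.1% |
| 86.1% | 6.2 / 6.2 | 73.6% | 17.5% | 60.7% | 4.6% | 12.9% | 21.8% |
| 70% | 6.9 / 6.9 | 55.5% | 27.6% | 40.1% | 12.3% | 15.3% | 32.2% |
| 87% | 6.2 / 8.0 | 74.0% | 11.9% | 65.2% | 3.1% | 8.8% | 22.9% |

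Across these inputs, morphine power is about 55–74% and methadone power about 12–33%. Morphine-only significance occurs in about 40–65% and is the commonest pattern in every row. This takes the methadone SD as no smaller than the morphine SD. In the reverse case (70% share, 6.9 / 6.2) it falls to 37% and is still the commonest.

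**Step 4. What a drug contrast could show.** SE_contrast = √(SE_morphine² + SE_methadone²), normal approximation, SD 6.2.
- 70% share: √(0.853² + 1.303²) = 1.56 days. The 95% half-width is 1.96 × 1.56 ≈ 3.1 days, power for a true 2-day difference between drugs is 25%, and 80% power needs 2.80 × 1.56 ≈ 4.4 days.
- 86.1% share: √(0.769² + 1.914²) = 2.06 days, with half-width 4.0 days, power 16%, and 5.8 days needed for 80% power.

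The posterior under the protocol's model cannot be computed, because neither document gives a mean or SD for the interaction priors.

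**The case against.** Several stronger readings are tempting, and the documents do not support them.

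- *The SAP created the separate drug tests.* It did not. Protocol 5.1.5 already has both subset analyses, numbered secondary outcomes 1 and 2. What the SAP loses is the Bayesian model planned alongside them, so replacing H2 and H3 by an interaction model would itself depart from the protocol.
- *Pooling the drugs was justified by the promise of this model.* Protocol 5.2.1 gives feasibility as the reason: about 1,000 infants could not be enrolled. The by-drug analyses were then added.
- *The trial can say nothing about a drug difference.* SAP 6.4.1 calls for a mean difference with a 95% CI for each normal regression, and the subsets do not overlap, so a contrast could be approximated by hand. What is missing is a prespecified one.
- *The model has been withdrawn.* The SAP cites protocol version 10. The protocol supplied has a change log running to version 11 and still contains 5.1.6. The two documents have simply not been reconciled.
- *Morphine-only significance is more likely than not.* It exceeds half only in some scenarios.

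Three further points stand. SAP 6.4.4 calls every analysis except the primary exploratory. The restored contrast would be weak (Step 4). And the opioid follows hospital practice (protocol 4.2.6) and is not randomised, so an arm-by-drug term is partly an arm-by-hospital-practice term, which a random hospital intercept does not remove.

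These points limit the claim but do not answer it. An analysis the protocol says will be done is absent from the SAP with no reason given, and SAP 3.5 keeps the goal it served.

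**Conclusion.** The point holds as an unexplained gap between protocol and SAP on an exploratory but stated goal. The primary comparison is untouched. If the effect is the same 2 days in both drugs, the planned pair of tests would most often (about 40–65%) return significance for morphine only, and both would be significant in about a fifth of trials at best in the tabulated scenarios. These figures assume the target of 302, SDs of 6.2 to 8.0 days, morphine shares of 70–87%, and simple two-sample comparisons without covariates or site effects. A smaller final N lowers both powers. As an assumed case, 200 infants at SD 6.2 gives about 48–56% for morphine and 13–24% for methadone (normal approximation, shares 70–86.1%). A shift toward methadone, which the protocol thinks possible, would narrow the gap between the two.

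A reader might infer that restoring the model would settle the drug question. It would not. Its value is in shrunken drug-specific estimates, intervals that show how little is known, and a direct probability of a difference in place of an informal comparison of p-values.

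**What to change.** 1. Keep the H2 and H3 subset analyses as prespecified.
2. Add the protocol 5.1.6 model to SAP 6.5: arm, drug, arm-by-drug interaction, drug-specific SDs and a hospital random effect. State numeric neutral and skeptical interaction priors before the data are analysed, because the protocol gives none. Report drug-specific effects with 95% credible intervals, and the probability that they differ, under both priors.
3. Add opioid type to the interaction analyses in SAP 6.4.4. Report the arm-by-drug contrast with its 95% CI whatever the interaction p-value, rather than applying the 0.10 reporting threshold.
4. State that any claim about a drug difference rests on that contrast and the posterior probability, not on setting the two p-values side by side.
5. If the omission was deliberate, record the decision and the reason in the SAP, and reconcile it with the protocol.

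**Cost.** One additional Bayesian model and one interaction term. The software, convergence checks and most priors are already in SAP 6.5.1, but choosing the interaction priors is new work. Three downsides should be stated with the results: the estimates will depend on those priors, especially with about 39 to 91 methadone infants (13–30% of 302); power for a 2-day drug difference is only about 16–25% at SD 6.2; and drug is confounded with hospital practice.
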